5.5 DISCONTINUATION OF THERAPY

If a patient is discontinued from study, the reason for discontinuation must be clearly documented in the source documentation and the EDC.

Study therapy for a given patient MUST immediately be discontinued for any the following reasons:

- Withdrawal of informed consent (subject's decision to withdraw for any reason)
- Any clinical adverse event, laboratory abnormality, inter-current illness, or clinical progression
 of disease which, in the opinion of the Principal Investigator, indicates that continued
 participation in the study is not in the best interest of the subject
- Pregnancy
- Termination of the study by the sponsor
- Imprisonment or the compulsory detention for treatment of either a psychiatric or physical (e.g., infectious disease) illness
- Any Grade 2 or greater adverse event (with the exception of worsening AD symptoms or injection site reactions) that is determined to be probably or definitely related to study drug administration.
- Any Grade 3 or greater injection site reaction
- Certain rescue treatments as specified in section 5.4

5.6 TRIAL STOPPING RULES

Enrollment of any further patients for the trial will be suspended for the following events:

- The death of a subject at any time during the trial that is deemed to be probably or definitely related to the administration of MABp1
- The occurrence of 2 or more serious adverse events occurring cumulatively and irrespective of dose cohort, that are probably or definitely related to the administration of MABp1

• Any significant safety finding assessed as probably or definitely related to MABp1 that in the opinion of the investigator warrants stopping the trial for additional assessment of safety.

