5.3 DOSE ESCALATION RULES

The sponsor will review safety data for all patients after the last patient in Group A has completed the week 4 visit or discontinued for any reason other than DLT. The sponsor will initiate escalation to the Group B dosing cohort after confirmation that no safety signals are identified and no study stopping rules have been met.

The National Cancer Institute Common Terminology Criteria for Adverse Events (NCI-CTCAE) v4.03 will be used to grade the severity of adverse events.

- Any AE (with the exception of worsening AD symptoms or injection site reactions) of grade 2 or higher that is probably or definitely related to study drug must be reported to the sponsor within 24 hours of learning of the event.
- Any grade 3 or greater injection site reaction must be reported to the sponsor within 24 hours of learning of the event.
- If three or more probably or definitely related grade 2 or greater AEs, and/or three or more grade 3 or greater injection site reactions occur in either group, dosing will be stopped for safety assessment.

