9.3 RECORDING OF ADVERSE EVENTS

All AEs and SAEs must be recorded on the case report form (CRF)/eCRF and in the patient's source documents occurring between visit 1 (post-injection) and visit 9 (or if subject terminates from study prior to visit 9, seven days after the last administration of bermekimab).

All AEs should be recorded in standard medical terminology as concisely as possible. The AE recorded should not be a procedure or a clinical/laboratory measurement but should reflect the event leading to the procedure or the cause of the clinical/laboratory abnormality, if known. Whenever possible, AEs should be evaluated and recorded as a diagnosis, rather than individual signs and symptoms. However, if a definitive diagnosis is not possible, the individual signs and symptoms should be recorded. Any AE that worsens in intensity, or becomes serious, should be recorded as a new event.

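### After a related death or two related SAEs, Section 5.6 suspends enrollment but states no hold on dosing, and those events alone need not meet the Section 5.3 dosing stop

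*Combined protocol and SAP*

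**What the plan says.** Section 5.6 has one operative sentence: "Enrollment of any further patients for the trial will be suspended for the following events". Three triggers follow. The first is a death judged probably or definitely related to drug. The second is "The occurrence of 2 or more serious adverse events occurring cumulatively and irrespective of dose cohort", with the same relatedness condition. The third is a significant related finding that, in the investigator's opinion, "warrants stopping the trial for additional assessment of safety".

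Section 5.3 holds the dosing rule. If three or more related grade 2+ adverse events (AEs), and/or three or more grade 3+ injection site reactions, "occur in either group, dosing will be stopped for safety assessment". The injection-site limb carries no relatedness condition. Section 5.3 also lets the sponsor open Group B only "after confirmation that no safety signals are identified and no study stopping rules have been met".

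Section 5.5 works patient by patient: "Study therapy for a given patient MUST immediately be discontinued" for listed reasons. These include a related grade 2+ AE in that patient, the Principal Investigator's judgment, and "Termination of the study by the sponsor".

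**The concern.** The two rules are out of order. The less grave pattern, three related grade 2 AEs in a group, carries an automatic dosing stop. The graver ones, a related death or two related SAEs, carry an automatic stop on enrollment only.

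Safety and tolerability is the primary endpoint and injections are weekly, so other patients' next doses fall due within about a week of a trigger. Whether they are given is left to someone deciding in time. An enrollment suspension also protects less as accrual proceeds. In Group A, a met rule at least blocks escalation. After the last Group B patient is enrolled there is nobody left to keep out and no cohort left to open.

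**Working it through.** The plan gives no operating characteristics for its stopping rules, and Section 10.2 says the sample size was one of convenience. There is no figure to reproduce. The check is whether events that meet Section 5.6 also meet Section 5.3, and whether another section closes the gap.

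**Inputs.** Section 5.6 thresholds: 1 related death, or 2 related SAEs pooled over cohorts. Section 5.3 threshold: 3 related grade 2+ AEs in a group. Synopsis: Group A, 9 patients, 4 weekly doses of 200 mg; Group B, 20 patients, 8 weekly doses of 400 mg.

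**Step 1: thresholds compared.** Assume one record per event, each SAE grade 2+, and no other counted events. Further related grade 2+ events needed in that group = 3 − count.

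| Events | 5.6 met | Count toward 5.3 | Further events needed |
|---|---|---|---|
| One related death | Yes | 1 | 3 − 1 = 2 |
| Two related SAEs, same group | Yes | 2 | 3 − 2 = 1 |
| One related SAE in each group | Yes | 1 and 1 | 3 − 1 = 2 in Group B |
| Three related grade 2 AEs, same group, none serious | No | 3 | 0: dosing stops |

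Pooling the Section 5.3 count over groups does not rescue the third row, since 1 + 1 = 2 is still below 3. That row also needs the Group A SAE not to have counted as a safety signal at the escalation review, or to have come after it. The latter is possible. The review follows the last Group A patient's week 4 visit, while Group A is followed to day 35. That leaves 35 − 28 = 7 days if the visit meant is visit 5, or 35 − 21 = 14 days if it is visit 4.

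**Step 2: what moves these counts.**
- Downward: earlier related grade 2+ AEs in the same group already count. Section 9.3 adds: "Any AE that worsens in intensity, or becomes serious, should be recorded as a new event". One course recorded at grade 2, then as worsened, then as serious gives 3 records, and 3 − 3 = 0. Section 5.3 may therefore be met at the same time as Section 5.6.
- Upward: Section 9.2 separates seriousness from severity, so an SAE can be grade 1. Such an SAE counts toward Section 5.6 but not toward the AE limb of Section 5.3.

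**Step 3: do other sections require a hold?**
- 5.5: stops the affected patient, acts on investigator judgment, or follows sponsor termination. Section 5.6 does not call for termination.
- 7 and 9.6: the sponsor hears of SAEs, and under Section 7 of most grade 2+ AEs, within 24 hours. This is reporting, not a hold.
- 11.2 and 11.3: notice to the IRB/EC, and deviation to remove an immediate hazard. Both are case by case.
- 11.12: who is told if the study is suspended or terminated, not when it must be.

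None ties a dosing hold for other patients to a Section 5.6 event.

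**Step 4: remaining exposure.** Section 5.6 does not define when enrollment is complete. Section 10.4 counts a patient as enrolled once dosed, so take completion as the last Group B patient's first dose. Then 8 − 1 = 7 doses remain, 7 × 400 mg = 2,800 mg, the last on day 7 × 7 = 49 (±2).

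The total still due to all unaffected patients depends on accrual, which the documents do not give. It can be 0, if the affected patient is the only one still on treatment.

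**The case against.** The strongest reply is that this is under-wording rather than a missing safeguard. The section is headed as trial stopping rules, its third trigger speaks of stopping the trial, and Section 5.3 refers to these as study stopping rules. Sponsor termination ends therapy for everyone, and Section 11.12 contemplates suspension. With 24-hour reporting, a sponsor that learned of a related death would very probably act before many more injections were given.

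Much of this stands. A wider stop may well have been intended, and the sponsor has the information and the power to impose one. But the operative sentence names enrollment only, and Section 5.3 shows that the authors wrote a dosing stop explicitly where they provided for one. If a wider stop was meant, the amendment only records it.

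The prior safety record also bears on urgency. Sections 9.7 and 1.1 report 831 treated patients, injection site or infusion reactions in 20 of them (2.4%), and only grade 1 events in the psoriasis and acne trials. This suggests triggers may be uncommon, but it supplies no related-SAE rate and does not change what happens if one occurs.

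A dosing hold on the third trigger would let one investigator's opinion stop injections at every site. That objection is sound, and the fix leaves the third trigger out.

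**Conclusion.** The gap is real and cheap to close. A related death alone, or two related SAEs alone, meets Section 5.6 without necessarily meeting Section 5.3, and no other section then requires a hold on other patients' dosing. With one record per event, SAEs of grade 2+ and nothing else counted, the group is still two events short of the dosing stop after a death, and one short after two SAEs in the same group. Earlier events or multiple records can reduce either figure to 0. The firmest exposure figure is per patient: up to 7 doses (2,800 mg) for the last Group B patient.

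A reader might infer three stronger things that the documents do not support.
- That the protocol directs dosing to continue after a death. It is silent, and the affected patient is off drug.
- That a large, calculable number of injections would follow. Without an accrual rate the total cannot be fixed and may be 0, so no range should be used to convey size.
- That the chance of a trigger can be estimated. The documents give no related-SAE rate.

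**What to change.** In Section 5.6, separate the first two triggers from the third. For a related death or two or more related SAEs, state: *enrollment and dosing of all enrolled patients will be suspended pending documented sponsor safety review*. In Section 5.3, add one line saying that dosing also stops when either of these events occurs. Leave any dosing hold under the third trigger to the sponsor's decision.

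Release remains a sponsor judgment without set criteria. What changes is the default: dosing is held unless the sponsor documents a reason to resume, rather than continuing unless someone intervenes.

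The cost is a short amendment to two sections, with no change to sample size and no effect if no trigger occurs. If one does, each patient on treatment may miss about one dose per week of review. That would cost some exposure, some of the pre-dose PK samples at visits 3, 5 and 8, and some visit 8 efficacy data, on which the secondary endpoints and the per-protocol set depend.

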6. CORRELATIVE STUDIES

6.1 PHARMACOKINETICS (PK) SAMPLE COLLECTION

An enzyme-linked immunosorbent assay (ELISA) has been developed to specifically measure bermekimab levels in human plasma. Blood will be drawn into a single 6 ml collection tube at each PK collection time point (pre-dose sample collection at visit 1, visit 3, visit 5, and visit 8). These samples will be collected per the study lab manual and immediately shipped to the Sponsor for PK analysis. The PK samples will also be used to test for the presence of antibodies against bermekimab and biomarker analysis.

7. ASSESSMENT OF SAFETY

Safety will be assessed by monitoring adverse events, vital signs, physical examinations, ECG and clinical laboratory measurements. All subjects who have received at least one dose of bermekimab will be included in the safety analysis. Adverse events will be monitored from Visit 1 (post-infusion) to Visit 9. Any serious adverse events or grade 2 or greater probably or definitely related events will be followed until resolution.

Study drug will be administered under close observation in a facility equipped to handle anaphylaxis. Subjects must be closely monitored until at least 1 hour following the administration of the antibody or 1 hour after their vital signs have stabilized.

Any AE (with the exception of worsening AD symptoms or injection site reactions) of grade 2 or higher must be reported to the sponsor within 24 hours of learning of the event. Any grade 3 or greater injection site reaction must be reported to the sponsor within 24 hours of learning of the event.

8. STUDY VARIABLES

8.1 DEMOGRAPHIC AND DISEASE CHARACTERISTICS

Demographic characteristics will include standard demography (age, sex, race, weight, and BMI), medical history, medication history, and prior biologic use for each patient. Characteristics of the patient's atopic dermatitis, including duration of disease, baseline EASI score (including individual signs score), baseline Investigator's Global Assessment, baseline body surface area involvement, baseline pruritus numerical rating score, baseline SCORAD score, baseline patient oriented eczema measure, baseline DLQI, and baseline HADS score, will be collected. *Baseline is defined as the visit 1 pre-injection assessment*.

8.2 STUDY ENDPOINT DEFINITIONS

Eczema Area and Severity Index

The EASI is a validated measure used in clinical practice and clinical trials to assess the severity and extent of AD. Four AD disease characteristics will be assessed for severity by the investigator or designee on a scale of "0" (absent) through "3" (severe). In addition, the area of AD involvement will be assessed as a percentage by body area of head, trunk, arms, and legs and converted to a score of 0 to 6.

Pharmacokinetic Assessment

An enzyme-linked immunosorbent assay (ELISA) has been developed to specifically measure bermekimab levels in human plasma. Blood will be drawn into a single 6 ml Na-Heparin collection tube at each PK collection time point (sample collection is pre-dose at visit 1, visit 3, visit 5, and visit 8). These samples will be collected per the study lab manual and immediately shipped to the Sponsor for PK analysis. The PK samples will also be used to test for the presence of antibodies against bermekimab.

Investigator's Global Assessment

The IGA is an assessment scale used in clinical studies to determine severity of AD and clinical response to treatment based on a 5-point scale ranging from 0 (clear) to 4 (severe).

Global Individual Signs Score

Individual components of the AD lesions (erythema, edema/papulation, excoriations, and lichenification) will be rated globally (ie, each assessed for the whole body, not by anatomical region) on a 4-point scale (from 0=none to 3=severe) using the EASI severity grading criteria.

CONFIDENTIAL

22 August 2018

PAGE 36 of 52

SCORing Atopic Dermatitis

The SCORAD is a validated tool used in clinical research and clinical practice that was developed to standardize the evaluation of the extent and severity of AD. There are 3 components to the assessment: A = extent or affected body surface area, B = intensity, and C = subjective symptoms. The extent of AD is assessed as a percentage of each defined body area and reported as the sum of all areas, with a maximum score of 100% (assigned as "A" in the overall SCORAD calculation). The intensity of 6 specific symptoms of AD (redness, swelling, oozing/crusting, excoriation, skin thickening/ lichenification, dryness) is assessed using the following scale: none (0), mild (1), moderate (2), or severe (3) (for a maximum of 18 total points, assigned as "B" in the overall SCORAD calculation). Subjective assessment of itch and sleeplessness is recorded for each symptom by the patient or relative on a VAS, where 0 is no itch (or sleeplessness) and 10 is the worst imaginable itch (or sleeplessness), with a maximum possible score of 20. This parameter is assigned as "C" in the overall SCORAD calculation. The SCORAD is calculated as: A/5 + 7B/2 + C where the maximum is 103.

Patient Assessment of Pruritus and Pain

The NRS is a simple assessment tool that patients will use to report the intensity of their pruritus (itch) and pain during a daily recall period using a study diary. Patients will be asked to complete the following questions:

- For average itch intensity: "On a scale of 0 to 10, with 0 being 'no itch' and 10 being the 'worst itch imaginable', how would you rate your itch **on average** during the previous 24 hours?"
- For maximum itch intensity: "On a scale of 0 to 10, with 0 being 'no itch' and 10 being the 'worst itch imaginable', how would you rate your itch at the **worst moment** during the previous 24 hours?"
- For pain intensity: "On a scale of 0 to 10, with 0 being 'no pain' and 10 being the 'most severe pain', how would you rate your pain **on average** during the previous 24 hours?"

Patients will be instructed to record their NRS score daily from day 0 to day 56 (+/-2). Sites will be expected to review the diary at each visit and enter the data from the previous 7 days.

Visit 1 Questionnaire for Pruritus, Pain and Erythema

The following questions assess the intensity of pruritus (itch) and pain experienced by the patient before and after the injection of bermekimab during visit 1. The patient will answer the following questions:

- 1. On a scale of 0 to 10, what is the current intensity of itch, with 0 being 'no itch' and 10 being the 'worst itch imaginable'.
- 2. On a scale of 0 to 10, what is the current intensity of pain, with 0 being 'no pain' and 10 being 'severe pain'.

The Investigator will assess the patient's Erythema and complete the following on the Visit 1 Questionnaire:

- 3. What is the current status of the patient's erythema overall?
- a. None \square Mild \square Moderate \square Severe \square
- b. Please describe area(s) and degree(s) of the patient's erythema in detail and if applicable any post-injection changes observed.

The Visit 1 Questionnaire will be performed twice:

- 1. Visit 1, pre-injection of bermekimab;
- 2. Visit 1, sixty minutes post-injection of bermekimab.

Patient Oriented Eczema Measure

The POEM is a 7-item, validated questionnaire used in clinical practice and clinical trials to assess disease symptoms in children and adults. The format is a response to 7 items (dryness, itching, flaking, cracking, sleep loss, bleeding, and weeping) based on frequency during the past week (ie, 0 = no days, 1 = 1 to 2 days, 2 = 3 to 4 days, 3 = 5 to 6 days, and 4 = every day) with a scoring system of 0 to 28; the total score reflects disease-related morbidity.

Hospital Anxiety and Depression Scale

The HADS is an instrument for screening anxiety and depression in non-psychiatric populations; repeated administration also provides information about changes to a patient's emotional state. The HADS consists of 14 items, 7 each for anxiety and depression symptoms; possible scores range from 0 to 21 for each subscale. The following cut-off scores are recommended for both subscales: 7 to 8 for possible presence, 10 to 11 for probable presence, and 14 to 15 for severe anxiety or depression.

Dermatology Life Quality Index

The DLQI is a 10-item, validated questionnaire used in clinical practice and clinical trials to assess the impact of AD disease symptoms and treatment on QOL. The format is a simple response (0 to 3 where 0 is "not at all" and 3 is "very much") to 10 questions, which assess QOL over the past week, with an overall scoring system of 0 to 30; a high score is indicative of a poor QOL.

CONFIDENTIAL

22 August 2018

9. ADVERSE EVENTS

9.1 DEFINITION OF ADVERSE EVENT (AE)

An adverse event is defined as any untoward medical occurrence in a subject participating in a clinical study that does not necessarily have a causal relationship with the pharmaceutical or biological agent under study. An AE can therefore be any of the following:

- Any unfavorable and unintended sign (including laboratory findings), symptom, or disease temporally associated with the use of bermekimab, whether or not it is apparently related to bermekimab
- A concurrent illness
- An exacerbation, or an unexpected increase in frequency or intensity of a preexisting condition, including intermittent or episodic conditions. However, anticipated day-to-day fluctuations or expected progression of the preexisting condition (based upon the Investigator's clinical judgment) are not to be considered AEs
- A significant or unexpected worsening of the condition/indication under investigation. However, anticipated day-to-day fluctuations or expected progression of the disease under investigation (based upon the Investigator's clinical judgment) are not to be considered AEs
- A suspected interaction between the investigational drug and concomitant medications
- Any clinically significant laboratory abnormality (including radiological interpretations, histopathological findings, etc.)

9.2 DEFINITION OF SERIOUS ADVERSE EVENT (SAE)

A serious adverse event is defined as any untoward medical occurrence that meets any of the following criteria:

- Results in death
- Life-threatening
- Requires or prolongs inpatient hospitalization
- Results in a persistent or significant disability
- Congenital anomaly/birth defect
- An important medical event that, while it may not result in death or be immediately lifethreatening or require/prolong hospitalization, may jeopardize the subject and/or may require medical or surgical intervention to prevent one of the outcomes listed above. Examples of such events are intensive treatment in an emergency room or at home for allergic

```
CONFIDENTIAL
```

bronchospasm; blood dyscrasias or convulsions that do not result in hospitalization; or the development of drug dependency or drug abuse.

Note that seriousness and severity should not be confused. A subject could experience a severe headache that would not qualify as an SAE, while another might experience a mild stroke that, while not severe, would be considered serious.

9.3 RECORDING OF ADVERSE EVENTS

All AEs and SAEs must be recorded on the case report form (CRF)/eCRF and in the patient's source documents occurring between visit 1 (post-injection) and visit 9 (or if subject terminates from study prior to visit 9, seven days after the last administration of bermekimab).

All AEs should be recorded in standard medical terminology as concisely as possible. The AE recorded should not be a procedure or a clinical/laboratory measurement but should reflect the event leading to the procedure or the cause of the clinical/laboratory abnormality, if known. Whenever possible, AEs should be evaluated and recorded as a diagnosis, rather than individual signs and symptoms. However, if a definitive diagnosis is not possible, the individual signs and symptoms should be recorded. Any AE that worsens in intensity, or becomes serious, should be recorded as a new event.

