The investigator initiated study enrolled patients with moderate to severe HS that were refractory to adalimumab. The study was double blind, randomized and placebo controlled, and utilized the

CONFIDENTIAL

22 August 2018

Hidradenitis Suppurativa Clinical Response (HiSCR) score as a primary endpoint. Ten patients were randomized to placebo and 10 patients to treatment with bermekiamb. A positive HiSCR score after 12 weeks was found in one (10%) and six (60%) patients respectively (OR: 13.50; 95%CIs: 1.19-152.61; p: 0.035). After withdrawal of therapy at week 12, a positive HiSCR score was found in nil (0%) and four (40%) patients after 24 weeks (p: 0.043).

Endogenous anti-IL-1 α antibodies are present in 5% to 28% of the general population^{4,5,6,7}. No negative correlations with disease have been noted for these individuals. To the contrary, the presence of natural anti-IL-1 α antibodies has been associated with favorable outcomes, both with respect to rheumatoid arthritis and ischemic heart disease. Animal studies also indicate that IL-1 α loss or antagonism does not result in harm. Moreover, the well-tolerated use of other approved biological agents that employ other strategies to block IL-1 activity suggest that bermekimab's targeting of IL-1 α represents a safe treatment approach.

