refrigeration and lay flat; allow to warm to room temperature. Do not heat

Pre-injection

- Concomitant medications/treatments
- o DLQI
- Urine pregnancy
- o EASI
- o IGA
- HADS
- Pruritus/Pain NRS: data from patient diary to be recorded at this time if available
- o SCORAD
- o POEM
- o GISS
- Vital signs (blood pressure, pulse, oxygen saturation, respiratory rate and body temperature)

Bermekimab subcutaneous injection in accordance with injection site determined by BMI at Screening

Post bermekimab subcutaneous injection

- 1 hour monitoring post-injection
 - Injection reaction
 - Vital signs (blood pressure, pulse, oxygen saturation, respiratory rate and body temperature) one hour post injection (70 +/- 10 minutes)
- Adverse event monitoring

Visit 8 (day 49 +/- 2)

> *At least 45 minutes before injection*: When using pre-filled syringes, remove syringe from

refrigeration and lay flat; allow to warm to room temperature. Do not heat

Pre-injection

- Concomitant medications/treatments
- Urinalysis
- Electrocardiogram (ECG) (patient should be supine for at least 5 minutes prior to performating ECG)
- Physical Examination
- o DLQI
- Urine pregnancy
- o EASI
- o IGA
- o HADS
- Pruritus/Pain NRS: data from patient diary to be recorded at this time if available
- o SCORAD
- o POEM
- o GISS
- Blood draw:
 - chemistry and hematology, 12.5mL
 - PK and Biomarker Analysis, 6mL
- Vital signs (blood pressure, pulse, oxygen saturation, respiratory rate and body temperature)

Bermekimab subcutaneous injection in accordance with injection site determined by BMI at Screening

Post bermekimab subcutaneous injection

- ➤ 1 hour monitoring post-injection
 - Injection reaction
 - Vital signs (blood pressure, pulse, oxygen saturation, respiratory rate and body temperature) one hour post injection (70 +/- 10 minutes)
- Adverse event monitoring

Visit 9 (56 +/- 2)

- Concomitant medications/treatments
- > DLQI
- Physical Examination
- ► EASI
- ► IGA
- > HADS
- > Pruritus/Pain NRS: patient diary to be retained and data to be recorded
- > SCORAD
- > POEM
- ➢ GISS
- Vital signs (blood pressure, pulse, oxygen saturation, respiratory rate and body temperature)
- Adverse Event Monitoring

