10.6.1 Analysis of Adverse Events

Adverse events reported in this study will be coded using the currently available version of MedDRA. Coding will be to lowest level terms. The verbatim text, the PT, and the primary SOC will be listed in patient listings.

Pre-treatment AEs are defined as those that develop or worsen in severity from the time the patient provides informed consent, prior to the first dose of study drug. Treatment emergent AEs (TEAEs) are defined as AEs that develop or worsen in severity following the first dose of study drug through the last study visit.

The number and percentage of patients experiencing AEs and TEAEs will be summarized by seriousness (SAEs), severity (grades 1-5), SOC, and PT.

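### Adverse event collection ends at visit 9 for completers, so a compliant Group B patient can have as few as 3 days of capture after the eighth dose, and Group A's end point is not stated

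*Combined protocol and SAP*

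**What the plan says.** Section 9.3 gives two rules for when recording of AEs and SAEs ends: "between visit 1 (post-injection) and visit 9 (or if subject terminates from study prior to visit 9, seven days after the last administration of bermekimab". The first applies to patients who stay in the study and is tied to a visit; the second applies to early leavers and is tied to the last dose. Section 7 gives only the first: "Adverse events will be monitored from Visit 1 (post-infusion) to Visit 9". Section 10.6.1 defines TEAEs as "AEs that develop or worsen in severity following the first dose of study drug through the last study visit", with no minimum time after the last dose.

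Section 5.1 sets "Visit 8 (day 49 +/- 2" days), and visit 9 at day 56 with the same tolerance. Both are counted from visit 1 as day 0, and no minimum interval between them is stated. The synopsis gives Group B (n=20) its eighth and last 400 mg injection at visit 8, and Group A (n=9) its fourth and last 200 mg injection at visit 4. Section 3 follows Group A for five weeks and six visits, so Group A has no visit 9.

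The plan uses 7 days after the last dose in four places: the one-week follow-up in the synopsis, the early-leaver rule in Section 9.3, the end of concomitant-medication recording in the Section 5.2 footnote, and the exposure formula in Section 10.7.1, which adds 7 days to the date of the last injection.

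**The concern.** For completers the end of collection moves with visit scheduling rather than with exposure. Two visits that each keep to their own window can be much closer together than the nominal week, so a patient who follows the protocol exactly can have less time observed after the last injection than the plan intends.

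Safety and tolerability is the only primary endpoint. After the eighth injection and its one-hour monitoring, visit 9 is the only scheduled contact. It includes a physical examination, vital signs and AE monitoring, but no chemistry, hematology, ECG or PK sample; these are last taken before the visit 8 injection. Reported AEs are therefore the main source of safety information after the highest cumulative exposure in the trial. An event that starts after an early visit 9 but within a week of the last dose falls outside every window the plan defines for a completer.

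Group A has a related gap. The cut-off is a visit that Group A does not attend under Section 3, so the text does not say when its collection ends.

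**Working it through.** This is date arithmetic on the visit windows in Sections 5.1 and 5.2 (±2 days throughout). No sample size formula applies.

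**1. The plan's own figure.** Nominal interval from the eighth dose to visit 9: 56 − 49 = 7 days, which reproduces the stated one-week follow-up. Screening, treatment and follow-up give 2 + 7 + 1 = 10 weeks, which matches the synopsis.

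**2. Group B, permitted range.** Visit 8 may fall on days 47 to 51 and visit 9 on days 54 to 58.
- Shortest: (56 − 2) − (49 + 2) = 54 − 51 = 3 days.
- Longest: (56 + 2) − (49 − 2) = 58 − 47 = 11 days.

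**3. All 5 × 5 = 25 permitted day pairs.**

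| Interval (days) | 3 | 4 | 5 | 6 | 7 | 8 | 9 | 10 | 11 |
|---|---|---|---|---|---|---|---|---|---|
| Pairs | 1 | 2 | 3 | 4 | 5 | 4 | 3 | 2 | 1 |

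Ten pairs are below 7 days, five equal 7 and ten are above. These are counts of what the windows allow, not probabilities. If all pairs were equally likely (an assumption), 10/25 = 40% would be below 7 days, or 8 of 20 patients. If 4% to 20% of patients were affected (also assumed), the number would be 0.8 to 4 of 20, roughly 1 to 4. The documents do not give actual visit timing.

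**4. Against the exposure formula.** A patient dosed on day 0 and last dosed on day 51 has a duration of exposure of (51 − 0) + 7 = 58 days. If visit 9 is on day 54, AE recording closes 58 − 54 = 4 days before the exposure period ends.

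**5. Group A, two readings.** The last dose (visit 4) falls on days 19 to 23.
- If collection ends at visit 6 (days 33 to 37): 33 − 23 = 10 to 37 − 19 = 18 days after the last dose, nominal 35 − 21 = 14.
- If Group A is treated as leaving before visit 9: 7 days.

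The text does not choose between these.

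**6. Effect of the proposed rule.** Taking the later of visit 9 and 7 days after the last injection, every Group B interval below 7 becomes 7 and the rest are unchanged, so the range is 7 to 11 days. If Group A's final visit is visit 6, its 10 to 18 days are unaffected.

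**The case against.** The best defence is that 3 days is one of 25 permitted pairs, the range is symmetric about the intended 7 days, and weekly dosing will keep most patients near that figure. This stands as far as it goes: the typical interval may well be 7 days, and the frequency of short ones is unknown. But visit 9 is not a dosing visit, so weekly dosing does not fix the interval before it. Sections 7 and 9.6 follow certain events to resolution or stabilization, but that covers events already recorded and does not extend the period in which a new event is captured. It is also true that Section 10.1 plans no formal test of the primary endpoint, so what is at stake is completeness of description, not an error rate.

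Several stronger readings are tempting, and the documents do not support them.

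- **TEAE percentages favour Group B.** TEAEs count from the first dose, so total observed time matters. Under Section 3, Group B is observed for 54 to 58 days and Group A for 33 to 37 (nominal 56 against 35). If Group A ended 7 days after visit 4, it would have 26 to 30. Crude percentages are therefore not shown to favour Group B; longer observation could raise them.
- **Early leavers always get 7 days.** Section 9.3 grants them 7 days of recording, but Section 10.6.1 ends TEAEs at the last study visit, and Sections 5.1 and 5.2 schedule no early-termination visit. An event on, say, day 5 after the last injection could be recorded and still fall outside the TEAE definition.
- **Group A is assured at least 10 days.** That holds only if its window ends at visit 6, which is not stated.
- **A 12-week safety window is needed.** In the cited hidradenitis trial, "a positive HiSCR score was found in nil (0%) and four (40%) patients after 24 weeks", twelve weeks after withdrawal. That is an efficacy response in another disease with 10 patients per arm. It shows neither drug persistence nor delayed toxicity, and gives no basis for the length of an AE window.
- **The window is the reason birth defects cannot be captured.** Section 9.2 lists "Congenital anomaly/birth defect" as a serious criterion, and no follow-up of pregnancies to outcome is described. That is fair comment but a separate matter, which a change of a few days would not address.

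**Conclusion.** The concern holds in a limited form. Section 9.3 uses a visit-based end for completers and a dose-based end for early leavers, Section 10.6.1 uses a third wording, and the visit windows allow a compliant Group B completer 3 to 11 days of capture after the eighth dose, nominally 7. The shortfall against the plan's own 7-day figure is at most 4 days per patient (7 − 3). It affects an unknown share of the 20 Group B patients. The end of Group A's window is not stated and could be 7 days, or 10 to 18 days, after its last dose.

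This rests on the ±2 day windows in Sections 5.1 and 5.2 applying independently to each visit, which is how they are written, and on Group A having six visits as Section 3 says. It does not show that the between-group comparison of TEAE percentages is biased in either group's favour, or that any delayed event is expected. It is a modest gap in capture for the sole primary endpoint, and worth closing because the remedy is cheap.

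**What to change.** Use one rule in Sections 7, 9.3 and 10.6.1. For both groups, AE and SAE collection and the TEAE window end at the later of the group's final visit and 7 days after the last injection. For a patient who leaves the study before that visit, keep the 7 days already in Section 9.3 and make Section 10.6.1 match. Name Group A's final visit explicitly.

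An alternative is to time the final visit from the actual last injection so that it cannot fall before day 7. The tolerance would then have to be one-sided, because day 7 ± 2 would still allow 7 − 2 = 5 days.

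The cost is protocol wording and, for patients whose final visit comes early, up to 4 more days of collection or one brief contact. No dose, injection schedule or treatment rule changes. Follow-up of pregnancies to outcome, if wanted, should be handled as its own item.
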